7.6 Sample Size Calculations

A sample size of 38 randomized patients in each treatment group (114 randomized patients overall) will provide 80% power to detect a between-group difference of 8.5 points in the UDysRS score with standard deviation of 13 points using a two-sided significance level of 0.05, using an ordinary least squares model. Assuming a drop-out rate of 15%, a total of 135 patients will be randomized. The sample size was calculated based on two sample t-test assuming equal variances in the two groups, using nQuery Advisor version 7.0.

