Each family of primary and secondary endpoints includes the comparison of each of the two dosages of pridopidine vs placebo. The overall Type I error rate within the family of each primary and secondary objective with respect to the two active dosages will be maintained by using the Hochberg's step-up method. According to Hochberg's step-up method, the higher of the two p-values will be compared to a two-sided significance level of 0.05. In case the higher p-value is <0.05 , both of the two comparisons will be judged as statistically significant. In case the higher p-value is not <0.05 , the lower p-value will be compared to a two-sided significance level of 0.025. In case the higher p-value is not <0.05 and the lower p-value is <0.025 , only the comparison related to the lower p-value will be judged as statistically significant. The testing will continue if at least one dose level was statistically significant in the previous family. Statistical significance will only be claimed if the dose level in question was statistically significant in the previous family.

In case not all endpoints are compared as a part of the hierarchical testing procedure, the statistical tests will be reported in any case and interpreted in an explorative manner.

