## 7 Sample Size Considerations

The sample size calculations for the study were based on 38 randomized subjects in each treatment group (114 randomized subjects overall) providing 80% power to detect a between-group difference of 8.5 points in the UDysRS score with standard deviation of 13 points using two sided significance level of 0.05. Assuming a drop-out rate of 15%, a total of 135 subjects were to be randomized. The sample size was calculated based on two sample t-test assuming equal variances in the two groups, using nQuery Advisor version 7.0.

Due to COVID-19 the study was terminated early.

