### 9.3 Interim Analyses and Data Monitoring

No interim analyses were planned.

Since the study was terminated prematurely before 30 subjects were enrolled no formal Drug Safety Monitoring Board (DSMB) meeting was conducted.

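### The protocol's 80% power is for one unadjusted comparison; under its own Hochberg rule, 38 evaluable per arm gives about 78% per dose if both doses work and 71–72% if only one does

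*Protocol*

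**What the plan says.** Protocol 7.6 (repeated in the synopsis) states that the planned size "will provide 80% power to detect a between-group difference of 8.5 points in the UDysRS score" and gives the design inputs. The effect is a "between-group difference of 8.5 points in the UDysRS score with standard deviation of 13 points"; the size is "A sample size of 38 randomized patients in each treatment group (114 randomized patients overall"); the level is stated as "using a two-sided significance level of 0.05, using an ordinary least squares model"; and "Assuming a drop-out rate of 15%, a total of 135 patients will be randomized". The same section says that the calculation used a two-sample t-test with equal variances.

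Protocol 7.9 sets the decision rule. If the larger of the two dose p-values is below 0.05, both doses succeed. Otherwise: "In case the higher p-value is not <0.05 , the lower p-value will be compared to a two-sided significance level of 0.025". At least one rejection in the primary family opens the gate to the secondary endpoints.

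SAP section 7 repeats the calculation in the past tense ("providing 80% power to detect a between-group difference of 8.5 points in the UDysRS score") and then notes early termination. SAP 9.3 adds: "Since the study was terminated prematurely before 30 subjects were enrolled". SAP section 2 says that the SAP prevails over the protocol where they differ, section 9.4 drops the multiplicity adjustment, and sections 8 and 14 add a pooled-dose contrast against placebo.

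**The concern.** The power statement and the test it is meant to support do not match. A dose with a p-value between 0.025 and 0.05 counts as a success in section 7.6, but under section 7.9 it succeeds only if the other dose is also below 0.05. A reader of 7.6 would take the chance of missing a true 8.5-point effect of a given dose to be 20%. If only one dose works, it is nearer 28–29% with 38 evaluable per arm. That case is not remote: Protocol 1.2.1.1 reads the macaque dose-response as pointing to greater efficacy at higher doses.

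A secondary matter is that SAP section 7 offers no power, detectable difference or expected precision for the trial actually analysed, including the pooled contrast. A reader of a null result finds only the design figure.

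**Working it through.** **Inputs.** From Protocol 7.6: difference 8.5, SD 13, 38 per arm, two-sided 0.05, drop-out 15%. From Protocol 5.1: allocation 1:1:1. From Protocol 7.9: the Hochberg rule.

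**1. The plan's own figure.** Non-centrality = 8.5 / (13 × √(2/38)) = 2.85, with 74 degrees of freedom and critical value 1.993. Power is 80.3%. Inflation: 114 / 0.85 = 134.1, which is 135 in three equal arms of 45. Both stated figures reproduce.

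**2. One effective dose, approximated at the 0.025 step.** With the same non-centrality and critical value 2.288, power is 71.2%. The full rule adds a little, because the ineffective dose occasionally also falls below 0.05.

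**3. Full Hochberg rule.** 1,000,000 simulated three-arm trials were run with a shared placebo arm. A dose succeeds if both p-values are below 0.05 or its own is below 0.025. Ranges run from pairwise to three-arm pooled variance.

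| True effects | Quantity | 38 per arm | 45 per arm |
|---|---|---|---|
| 8.5 and 8.5 | each dose | 77.8–78.1% | 84.9–85.2% |
| 8.5 and 8.5 | both doses | 69.2–69.7% | 78.2–78.6% |
| 8.5 and 8.5 | at least one | 86.4–86.6% | 91.7–91.8% |
| 8.5 and 0 | the effective dose | 71.6–72.1% | 79.6–80.0% |
| 8.5 and 4.25 | the 8.5-point dose | 72.7–73.0% | not run |

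The 45-per-arm column treats every randomised patient as contributing fully. It is an upper bound on the contribution of drop-outs' partial data.

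For scale: 80% at the 0.025 step takes 46 evaluable per arm (80.2%), that is 138, or 138 / 0.85 = 162.4, so 163 randomised.

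**4. The terminated trial (assumed arm sizes).** The documents give neither the number enrolled nor the split by arm. Assume a near-equal split of at most 29 patients, SD 13, a true difference of 8.5, and the SAP's unadjusted 0.05. The 95% CI half-width is t × 13 × √(1/n₁ + 1/n₂).

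| Contrast | n | Power | Difference detectable with 80% power | CI half-width |
|---|---|---|---|---|
| One dose vs placebo | 9 vs 9 | 25.7% | 18.3 | 13.0 |
| One dose vs placebo | 10 vs 10 | 28.3% | 17.2 | 12.2 |
| Pooled vs placebo | 18 vs 9 | 33.8% | 15.5 | 10.9 |
| Pooled vs placebo | 19 vs 10 | 36.5% | 14.8 | 10.4 |

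With 7 per arm, power is 20.3% per dose and 26.9% pooled (14 vs 7). With 5 per arm it is 15.0% and 19.8% (10 vs 5).

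**The case against.** The strongest reply is that section 7.6 contains no arithmetic error. It names its test, its level and its inputs, and every figure follows from them. That stands: the fault is an omission, a mismatch with section 7.9.

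Second, the protocol's gate opens on at least one rejection, and that power is about 86% if both doses work. This also stands, so it would be too strong to say that the design fails to deliver 80% on any definition. When both doses work, the per-dose shortfall is only about 2 points.

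Third, the planned analysis is a repeated-measures model with a baseline covariate, on a set that includes drop-outs with some post-baseline data. True power therefore probably lies above the 38-per-arm column. Any gain from baseline adjustment or correlation between visits cannot be computed, because the documents give no correlation. This softens the size of the point but does not make the unadjusted figure the right one to quote.

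Fourth, the SAP supersedes the protocol and tests without adjustment, so the Hochberg shortfall concerns the design only and not the analysis now planned. That is correct.

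A reader might also infer that the SAP claims 80% power for the terminated trial. It does not. SAP 7 reports the figure in the past tense as the original calculation and follows it with the early termination. SAP 3 warns that arms may be too small, SAP 4 recasts the study as proof of concept, and SAP 9.4 makes p-values primarily descriptive. The 95% confidence intervals in SAP 14.1 will show directly whether 8.5 points is excluded.

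**Conclusion.** The point holds as a reporting gap in the design power. The 80% in Protocol 7.6 is unadjusted, while the protocol's confirmatory rule is Hochberg across two doses. With 38 evaluable per arm, the loss against 80.3% is about 2 points per dose if both doses work and 8–9 points if only one does. The chance of winning on both doses is about 69%. At-least-one-dose power is above 80% if both work. If all 45 per arm contributed fully, the per-dose figures would rise to about 85% and 80%. All of this rests on the protocol's 8.5 points and SD of 13, and on a t-test in place of the planned model.

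For the terminated trial, power at 8.5 points is at most about 26–28% per dose and 34–36.5% pooled. This is a near-upper bound on assumed arm sizes: the EE1 and EE2 criteria (on treatment, 80% dosing or compliance) can only reduce n, and the calculation carries the design effect and SD over to Visits 3 and 5. It is a limitation worth stating. It is not an inconsistency in the SAP.

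**What to change.** Wherever the design power is reported (Protocol 7.6 and synopsis, SAP 7, the clinical study report), say that 80% refers to one dose against placebo without multiplicity adjustment. Beside it, give the Hochberg power per dose if both work, for the effective dose if only one works, for both doses and for at least one, and state the number of evaluable patients assumed. This needs no extra patients and no change to any analysis; the cost is a less favourable headline number.

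As a secondary suggestion only, SAP 7 could say explicitly that 80% is the superseded design figure. It could add the detectable difference or expected confidence-interval half-width for the each-dose and pooled contrasts at the actual arm sizes. That costs a short calculation once those sizes are known.

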7.7 Analysis Sets

The following analysis sets will be used in the statistical analyses.

Intent-to-Treat (ITT) Set: The ITT set will include all randomized patients. The patients will be grouped as randomized. Retrieved drop-out data (data captured from the drop-outs after the end-of-study visit when the patient is free of study treatment) will not be included in the ITT set. The ITT set will be used for the sensitivity analysis of the primary endpoint.

Modified Intent-to-Treat (mITT) Set: The mITT set will include all randomized patients who receive a dose of study treatment and have efficacy assessments both at Baseline (Visit 2) and at least one post-randomization time point. The patients will be grouped as randomized. Retrieved drop-out data (data captured from the drop-outs after the end-of-study visit when the patient is free of study treatment) will not be included in the determination of the mITT set. The mITT set will be used for the efficacy analysis.

Completer Set: The completer set is a subset of the mITT set and includes the subsets of patients with efficacy data at Visit 7/ET.

The patients will be grouped as randomized. The completer set will be used for the sensitivity analysis of the primary endpoint.

Safety Set: The safety set will consist of all patients receiving at least one dose of study treatment. The patients will be grouped according to the treatment regimen actually received at Visit 3. The safety set will be used for the safety analyses.

PK Set: The PK set will consist of all patients in the safety set with at least one pridopidine concentration sample result reported. The PK set will be used for the PK analyses.

7.8 Description of Subgroups to be Analyzed

Subgroup analyses may be conducted as deemed necessary and will be defined in the SAP.

[figure not shown]
7.9 Statistical Analysis Methodology

Statistical analysis will be performed using SAS software Version 9.3 or later. Continuous variables will be summarized using the mean, the standard deviation, median, minimum value, and maximum value. Categorical variables will be summarized using frequency counts and percentages. All collected data will be listed in data listings.

Each primary and secondary endpoint includes the comparison of each of the two dosages of pridopidine vs placebo. The overall Type I error rate within the family of each primary and secondary endpoint will be maintained by using the Hochberg's step-up method. Furthermore, the primary and secondary endpoint families will be evaluated in a hierarchical manner as outlined above. For this purpose, a matched parallel gatekeeping procedure will be used.

The testing strategy is summarized in [Figure 2](#) and detailed below.

Figure 2 **Summary of the Statistical Testing Strategy**

The primary endpoint family (F_1) consists of two null hypotheses H_{11} and H_{12} for comparisons of pridopidine 100 mg BID and pridopidine 150 mg BID, respectively, with placebo in regard to the primary endpoint. That is, $F_1 = \{H_{11}, H_{12}\}$. Similarly, the first secondary endpoint family $F_2 = \{H_{21}, H_{22}\}$ consists of H_{21} and H_{22} for comparisons of pridopidine 100 mg BID and pridopidine 150 mg BID, respectively, with placebo in regard to the secondary endpoint ranked first in the hierarchy. The family F_1 serves as a gatekeeper for F_2 such that F_2 will be examined only when the gatekeeper F_1 has been successfully passed, i.e., at least one of the hypotheses in the F_1 family is rejected. The significance in the secondary endpoint ranked first for a dose level cannot be claimed unless its corresponding primary hypothesis is significant. The same procedure will continue to the next families of secondary endpoints according to the hierarchy defined for the endpoints. The procedure will go on as long as the previous gatekeeper has been successfully passed.

Each family of primary and secondary endpoints includes the comparison of each of the two dosages of pridopidine vs placebo. The overall Type I error rate within the family of each primary and secondary objective with respect to the two active dosages will be maintained by using the Hochberg's step-up method. According to Hochberg's step-up method, the higher of the two p-values will be compared to a two-sided significance level of 0.05. In case the higher p-value is <0.05 , both of the two comparisons will be judged as statistically significant. In case the higher p-value is not <0.05 , the lower p-value will be compared to a two-sided significance level of 0.025. In case the higher p-value is not <0.05 and the lower p-value is <0.025 , only the comparison related to the lower p-value will be judged as statistically significant. The testing will continue if at least one dose level was statistically significant in the previous family. Statistical significance will only be claimed if the dose level in question was statistically significant in the previous family.

In case not all endpoints are compared as a part of the hierarchical testing procedure, the statistical tests will be reported in any case and interpreted in an explorative manner.

7.9.1 Analysis of Primary Endpoint

The primary endpoint will be analyzed using a Mixed Model for Repeated Measures (MMRM) with no imputation using the mITT population. The Baseline (Visit 2) score will be included as a covariate and the treatment group (pridopidine 100 mg BID, pridopidine 150 mg BID or placebo), Visit 4, Visit 5, Visit 6 or Visit 7/ET, and the interaction between treatment group and visit as fixed factors in the MMRM. An unstructured covariance structure will be applied for MMRM. In case the model will not converge with the unstructured covariance structure, the heterogeneous Toeplitz structure (TOEPH) will be used instead. In case the model will not converge with the heterogeneous Toeplitz structure, heterogeneous compound symmetry will be used. The denominator degrees of freedom will be computed using the Kenward-Roger method. The difference between each dosage of pridopidine vs placebo at Visit 7/ET along with the 95% CIs and associated p-value will be estimated from the MMRM. The differences at Visit 4 and Visit 6 will be estimated as well from the same model.

Sensitivity analyses of the primary endpoint will be conducted in the ITT set with multiple imputation methods, both assuming that data are missing at random and not missing at random. The analysis assuming that data are not missing at random will be conducted with the Copy-Reference approach, i.e., assuming that the patients who have missing data will follow the trajectories of the placebo-treated patients after the first visit with missing data. Further sensitivity analysis will be conducted in the completer set with MMRM. In addition, sensitivity analyses will be conducted by including the retrieved drop-out data (data captured from the drop-outs after the end-of-study visit when the patient is free of study treatment) to the mITT analysis. All efforts will be made to perform scheduled efficacy assessments after patients discontinue.

7.9.2 Analysis of Secondary Endpoint

The continuous secondary endpoints (sum scores derived from UDysRS, UPDRS, and endpoints based on the “ON/OFF” home diaries) will be analyzed with MMRM models similar to those used for analysis of the primary endpoint. The mITT population will be used for these analyses.

The categorical secondary endpoints (proportion of responders and proportion of patients improving based on PGI-C or CGI-C) will be analyzed in the mITT population using the generalized linear mixed model (using the GLIMMIX from SAS for binomial data with logit link). This analysis will model the response data from each postbaseline visit with treatment group (pridopidine 100 mg BID, pridopidine 150 mg BID or placebo), visit (Visit 4, Visit 5, Visit 6 or Visit 7/ET), and interaction between the treatment group and visit. An unstructured covariance structure will be used for the repeated measures model. In case the model will not converge with the unstructured covariance structure, the heterogeneous Toeplitz structure will be used instead. In case the model will not converge with the heterogeneous Toeplitz structure, heterogeneous compound symmetry will be used instead. The odds ratio for the treatment difference, 95% CIs for the odds ratio and p-value will be provided.

7.9.3 Pharmacokinetic Analyses

The PK analysis will be conducted on the PK set. Plasma concentrations of pridopidine and its metabolite TV-45065 will be listed and summarized by visit and time point. Descriptive statistics will include the mean, coefficient of variation, geometric mean, minimum, median, and maximum. Relationships between plasma concentrations of pridopidine and TV-45065 at Visit 4, Visit 6, and Visit 7/ET vs key safety and efficacy measures will be explored graphically. Additional details will be provided in the SAP.

7.9.4 Safety Analyses

The safety analysis will be conducted on the safety set. The AEs will be coded according to the MedDRA and treatment-emergent adverse events (TEAEs) summarized by treatment group, system organ class and preferred term. Further summaries will be done by seriousness, severity, relationship to study treatment and actual dose at the time of onset.

Vital signs, ECG data and laboratory tests at baseline (last non-missing results prior to the first dose of study drug, each postbaseline visit, and changes from baseline to each of the postbaseline visits will be summarized with descriptive statistics. Shift tables for the laboratory tests based on a classification of values as low, normal, or high with respect to the reference range will be summarized.

For vital signs, orthostatic hypotension is defined as a reduction of 20 mmHg or more in systolic blood pressure, or a reduction of 10 mmHg or more in diastolic blood pressure, for the standing measurement compared to the supine measurement. The proportion of patients with orthostatic hypotension will be summarized with shift tables.

Prilenia Therapeutics

Protocol: PL101-LID201 Protocol Amendment 1/v2.0

Pridopidine

19 Nov 2019

For ECG data, absolute QTcF of >450 msec, >480 msec, and >500 msec, changes from baseline in QTcF>30 msec and <60 msec, and changes in QTcF>60 msec throughout the study will be summarized.

All other safety data will be summarized with descriptive methods.

7.9.5 Interim Analyses

No interim analyses are planned for the study.

8 Data Quality Assurance

This study will be conducted according to the International Council for Harmonisation (ICH) E6 (R2) risk and quality processes described in the applicable procedural documents. The quality management approach to be implemented in this study will be documented and will comply with the current ICH guidance on quality and risk management (ICH Q9).

8.1 Data Management

As part of the responsibilities assumed by participating in the study, the investigator agrees to maintain adequate case histories for the patients treated as part of the research under this protocol. The investigator agrees to maintain accurate eCRFs and source documentation as part of the case histories. These source documents may include, but are not limited to, diary cards/laboratory reports/ECG strips/rater scales, etc.

Investigative site personnel will enter patient data into Medidata RAVE. The analysis data sets will be a combination of these data and data from other sources (e.g., laboratory data).

Clinical data management will be performed in accordance with applicable Prilenia Therapeutics standards and data cleaning procedures to ensure the integrity of the data, e.g., removing errors and inconsistencies in the data. Adverse event terms will be coded using the MedDRA, an internal validated medical dictionary, and concomitant medications will be coded using the World Health Organization Drug Dictionary (WHODRUG).

After database lock, each study site will receive a CDROM containing all of their site specific eCRF data as entered into Medidata RAVE for the study, including full discrepancy and audit history. Additionally, a CDROM copy of all of the study site's data from the study will be created and sent to the sponsor for storage. [REDACTED] will maintain a duplicate CDROM copy for their records. In all cases, patient initials will not be collected or transmitted to the sponsor.

9 Ethics

9.1 Independent Ethics Committee or Institutional Review Board

Federal regulations and the ICH guidelines require that approval be obtained from an IRB/ IEC before participation of human patients in research studies. Before study onset, the protocol, informed consent, advertisements to be used for the recruitment of study patients, and any other written information regarding this study to be provided to the patient or the patient's legal guardian must be approved by the IRB/IEC. Documentation of all IRB/IEC approvals and of the IRB/IEC compliance with ICH harmonized tripartite guideline E6 (R2): Good Clinical Practice (GCP) will be maintained by the site and will be available for review by the sponsor or its designee.

All IRB/IEC approvals should be signed by the IRB/IEC chairman or designee and must identify the IRB/IEC name and address, the clinical protocol by title or protocol number or both, and the date approval or a favorable opinion was granted. The investigator is responsible for providing written summaries of the progress and status of the study at intervals not exceeding 1 year or otherwise specified by the IRB/IEC. The investigator must promptly supply Prilenia Therapeutics or its designee, the IRB/IEC, and, where applicable, the institution, with written reports on any changes significantly affecting the conduct of the study or increasing the risk to patients.

